4.1.1 Definitions

Baseline

Unless stated otherwise, for each subject, baseline value of a parameter (e.g., efficacy laboratory parameter, safety laboratory test, ECG or physical measurement endpoint) is defined as the last assessment on or prior to the date of the first dose of the double-blind study medication in the ST treatment period (Day 1).

If there are multiple assessments with the same date and time, the average value will be used as baseline.

For subjects belonging to the Randomised Withdrawal Subjects Data Set, the withdrawal baseline value for a given parameter is defined as the closest available value on or before the day of first dose in the Randomised Withdrawal period.

Change from baseline

Change from baseline to any Week t in the analysis period (i.e., ST treatment period and ST+LT treatment period) is defined as follows:

$C_{Week\ t} = M_{Week\ t} - M_{baseline}$,
where:

- $C_{Week\ t}$ is the change from baseline at Week t ,
- $M_{Week\ t}$ is the measurement at Week t ,
- $M_{baseline}$ is the measurement at baseline.

The “Week t ” to which a measurement belongs is determined using the conventions described in [Table 8](#) (Section 4.1.6).

Last observation carried forward (LOCF)

A post-baseline missing value will be imputed by the last available non-missing post-baseline or post-withdrawal baseline (as applicable) value. If the first scheduled post-baseline or post-withdrawal baseline value is missing, no imputation will be done.

Day 1 is the date of first dose of study drug in the ST period.

Study day is defined relative to the date of first dose (Day 1) received in ST treatment period, and is calculated as:

- If assessment date is before the date of first dose: assessment date - date of first dose in the ST period (Day 1).
- If assessment date is on or after the date of first dose: assessment date - date of first dose in the ST period (Day 1) + 1.

Treatment response to HbA1c

A treatment responder at Week t is a subject with HbA1c $< 7\%$ at Week t (irrespective of baseline value). HbA1c response at Week t will be derived by dichotomising HbA1c values at Week t (binary variable, set to 1 if HbA1c $< 7\%$ at Week t and 0 if HbA1c $\geq 7\%$ at Week t). Where specified, missing HbA1c responses at Week t will be derived from imputed continuous values of HbA1c for Week t .

Rescue medication initiation

Rescue medication initiation is defined as the first date/time of rescue insulin recorded on the Rescue Insulin eCRF. Partial rescue insulin start dates are imputed as defined in Appendix 8.4.

Prior to rescue medication initiation

An assessment or event is defined as prior to rescue if the date/time of the assessment or event occurred prior to the date/time of first rescue medication. If the assessment or event only has date collected, then prior to rescue includes assessments or events that occurred on the day of first rescue medication.

Subjects may have been rescued (i.e. had a rescue visit per the protocol guidance), but have not had their insulin dose increased if they were on background insulin or started insulin if they were on background metformin only, if their high HbA1c or FPG results meeting the rescue criterion were managed by diet and exercise. These subjects who did not start or increase total daily insulin dose after the rescue visit and is thus not recorded on the Rescue Insulin eCRF will be included in the sensitivity analyses.

4.1.2 Descriptive summaries of continuous variables

Descriptive summary statistics for continuous variables will include: number of non-missing records n , mean, standard deviation (SD), median, minimum and maximum. If appropriate, 1st and 3rd quartiles will also be presented. For PK plasma concentrations, summary statistics will additionally include geometric mean, geometric SD (following back transformation of a log transformed geometric mean) and the coefficient of variation (CV%).

Data reporting details (such as number of decimals) are provided in the Appendix (Section 8.12).

4.1.3 Descriptive summaries of categorical variables

Categorical data will be summarised for each treatment group or regimen as the number and percentage of subjects in each category. Percentages will be calculated out of the total number of subjects in the analysis set (and treatment group as appropriate) for the variable summarised.

Weighted proportions will be calculated as the weighted count of subjects with the event out of the total number of weighted subjects in the analysis set (and treatment group as appropriate).

4.1.4 Summaries of shift in categorical variables

Descriptive summaries of change from baseline in selected categorical variables will be provided using shift tables. Only subjects with baseline and post-treatment or post-study/follow-up (as applicable) assessments will be included in the shift table summaries. Frequencies and percentages of subjects within each treatment group or regimen will be generated for levels of cross-classifications of baseline, the on-treatment value and the post-study/follow-up value (if applicable) of the parameter. The on-treatment value can either be the value at a certain time point, or (for example, laboratory tests) the minimum/maximum value in the direction of toxicity which has been observed during the analysis period. Summaries of shifts will only include the frequency and percentage of subjects by shift category and treatment group. No differences in these percentages between treatment groups or regimens will be assessed.

4.1.5 Treatment regimens

The following treatment regimens are considered for analysis:

- Low-dose/high-dose: Initial treatment of the low-dose (5 mg of dapagliflozin or 2.5 mg of saxagliptin) followed by up-titrating to the high-dose (10 mg of dapagliflozin or 5 mg of saxagliptin) for those who do not achieve the glycaemic target of HbA1c < 7% at Week 12 (not responding and re-randomised to high-dose) and continuing treatment with the low-dose for those achieving the glycaemic target of HbA1c < 7% at Week 12 (responding and not re-randomised; Groups I & III in [Figure 1](#)).
- Low-dose: Initial treatment of the low-dose (5 mg of dapagliflozin or 2.5 mg of saxagliptin) followed by continuing treatment on the low-dose drug for those who do not achieve the glycaemic target of HbA1c < 7% at Week 12 (not responding and re-randomised to low-dose) and those achieving glycaemic target of HbA1c < 7% at Week 12 (responding and not re-randomised; Groups I & II in [Figure 1](#)).
- Placebo, all subjects randomised to placebo.

Subjects who are receiving background medication with insulin only, or metformin + insulin (and who are therefore not eligible for the third randomisation) will continue with their randomised study medication assigned after the Week 12 assessment in the double-blind LT treatment period. After completion of assessments at Week 26, a subset of eligible subjects who are receiving background medication with metformin only will undergo a third randomisation (randomised withdrawal of background medication) at either Week 32 or Week 40. The following treatment comparisons are considered for this analysis:

- For subjects initially randomised to dapagliflozin (or saxagliptin): Initial treatment of the overall (combined low-dose and high-dose) dapagliflozin (or saxagliptin) with metformin compared to high-dose dapagliflozin (or saxagliptin) without metformin.
- For subjects initially randomised to placebo: Initial treatment of the placebo with metformin compared to high-dose dapagliflozin (or saxagliptin) without metformin.
- For all subjects, regardless of initial randomisation, based on third randomisation (for AE and marked abnormality [MA] laboratory analysis only).

For Week 104 analyses, subjects will be summarised based on both the first and last treatment received and also repeated for the subset of Week 104 completers (subjects who had the Week 104 visit).

Refer to Appendix 8.13 for full details on the presentation of the treatment labels for the analysis.

4.1.6 Treatment and dose assignments

For dose at onset analyses, subjects will be presented under the treatment and dose received.

For assessments taken on the day of the planned dose change (Week 14, Week 32/40 [if subject underwent the third randomisation]), subjects will be assigned to the previous dose. For events (adverse events) that occurred on the day of the planned dose change, subjects will be assigned to the new dose.

For PK analyses, subjects will be presented under the treatment and dose received on the day of the assessment.

4.1.7 Data summaries and listings

Dapagliflozin and saxagliptin will be summarised separately. For demographics and efficacy analyses, analyses will be presented by treatment regimen (low-dose, low-dose/high-dose). In addition, for demographics, and (where specified) efficacy analyses, analyses will also be provided for overall drug (combining all doses of each drug). For safety analyses, analyses will be presented by overall drug. The common placebo group will be included in each summary.

Demographics and efficacy analyses will be based on the Randomised Subjects Data Set and the randomised treatment assignment. Selected demographics and efficacy summaries and analyses will also be provided for the Up-titration Randomised and Randomised Withdrawal Subjects Data Sets. In addition to the analyses based on the Randomised Subjects Data Set, a sensitivity analysis of the primary efficacy endpoint will be performed using the Evaluable Subjects Data Set if greater than 10% of subjects of any treatment or placebo have RPDs. Safety analyses will be based on the Treated Subjects Data Set and the actual treatment assignment.

In addition, within the analyses of dapagliflozin and saxagliptin separately, the overall (combined low-dose and high-dose) efficacy and safety analyses will be repeated for the subgroup of subjects on a stable baseline dose of metformin IR or XR (with or without insulin). For these analyses, the dapagliflozin or saxagliptin treatment groups will be combined and compared to the (common) placebo group.

Data summaries and specific analyses by study period will be restricted to the cut-off dates defined in Table 8. Comparisons are based on onset dates for events and the date of assessment for other parameters (laboratory tests, vital signs etc.). The ST and ST+LT periods start from Baseline (day of first dose in the ST period) and the Randomised Withdrawal period starts from Randomised Withdrawal Baseline (day of first dose in the Randomised Withdrawal period).

The time is included in the comparisons only if both dates being compared have the time provided.

For those data which will be listed, each subject will appear in the listings with their subject identifier, age, sex, race and background medication. Only subjects with data available will be presented in the listings. If a visit took place but no data is entered for the type of assessment being listed (other than 'Not Done'), the entry will not be listed. Subject data listings will be sorted by subject identifier, treatment group, dose (low, low/high) as per first randomisation, up-titration, and third randomisation, and if applicable, parameter group, parameter name, nominal visit name, analysis visit name (Baseline, Week 2, etc.), visit date and date/time of assessment (with corresponding day relative to first dose), unless specified otherwise. Events that occurred after first rescue medication use will be flagged in the efficacy listings.

Table 8 Cut-off dates for analyses by analysis type and study period

Data	Analysis type*	ST period ^a	ST+LT period ^a	Randomised withdrawal period ^{a,e}
Safety analyses				
AE, non-serious DKA	Prim	
 Start of LT period (if applicable) Date of last dose during the ST period + 4 days^b 	
 Week 52/ETD date + 4 days^b 	
 Week 52/ETD date + 4 days^b
	Sens	
 Start of LT period (if applicable) Date of last dose during the ST period + 4 days^b First rescue intake^d 	
 Week 52/ETD date + 4 days^b First rescue intake^d Week 32^f/ETD date + 4 days^b Week 32^f/ETD date + 4 days^b First rescue intake^d 	
 Week 52/ETD date + 4 days^b First rescue intake^d
SAE (including serious DKA, serious Hypoglycaemia)	Prim	
 Start of LT period (if applicable) Date of last dose during the ST period + 30 days^b 	
 Week 52/ETD date + 30 days^b 	
 Week 52/ETD date + 30 days^b
	Sens	
 Start of LT period (if applicable) Date of last dose during the ST period + 30 days^b First rescue intake^d 	
 Week 52/ETD date + 30 days^b First rescue intake^d Week 32^f/ETD date + 30 days^b Week 32^f/ETD date + 30 days^b First rescue intake^d 	
 Week 52/ETD date + 30 days^b First rescue intake^d
Non-serious Hypoglycaemia	Prim	
 Start of LT period (if applicable) Date of last dose during the ST period + 4 days^b First rescue intake^d 	
 Week 52/ETD date + 4 days First rescue intake^d 	
 Week 52/ETD date + 4 days First rescue intake^d
	Sens	
 Start of LT period (if applicable) Date of last dose during the ST period + 4 days^b 	
 Week 52/ETD date + 4 days Week 32^f 	
 Week 52/ETD date + 4 days
Safety laboratory tests (excl. liver function)	Prim	
 Start of LT period (if applicable) Date of last dose during the ST period + 4 days 	
 Week 52/ETD date + 4 days 	
 Week 52/ETD date + 4 days
	Sens ^c	
 Start of LT period (if applicable) Date of last dose during the ST period + 4 days First rescue intake^d 	
 Week 52/ETD date + 4 days First rescue intake^d Week 32^f/ETD date + 4 days Week 32^f/ETD date + 4 days First rescue intake^d 	
 Week 52/ETD date + 4 days First rescue intake^d
Liver function tests	Prim	
 Start of LT period (if applicable) Date of last dose during the ST period + 30 days 	
 Week 52/ETD date + 30 days 	
 Week 52/ETD date + 30 days

Data	Analysis type*	ST period ^a	ST+LT period ^a	Randomised withdrawal period ^{b,c}
Safety analyses				
Vital signs, ECG, Growth markers	Prim	
 Start of LT period (if applicable) Date of last dose during the ST period + 4 days 	
 Week 52/ETD date + 4 Days 	
 Week 52/ETD date + 4 days
Body weight, Height, BMI, Tanner staging	Prim	
 Start of LT period (if applicable) Date of last dose during the ST period + 8 days 	
 Week 52/ETD date + 8 days 	
 Week 52/ETD date + 8 days
UACR, Urinary glucose	Prim	
 Start of LT period (if applicable) Date of last dose during the ST period + 1 day 	
 Week 52/ETD date + 1 day 	
 Week 52/ETD date + 1 day
Efficacy analyses				
	Prim	
 Start of LT period (if applicable) 	
 Week 56/EOS date 	
 Week 56/EOS date
HbA1c	Sens	
 Start of LT period (if applicable) Date of last dose during the ST period + 8 days First rescue intake^d 	
 Week 52/ETD date + 8 days First rescue intake^d 	
 Week 52/ETD date + 8 days First rescue intake^d
	Prim	
 Start of LT period (if applicable) 	
 Week 56/EOS date 	
 Week 56/EOS date
FPG	Sens	
 Start of LT period (if applicable) Date of last dose during the ST period + 1 day First rescue intake^d 	
 Week 52/ETD date + 1 day First rescue intake^d 	
 Week 52/ETD date + 1 day First rescue intake^d

*Prim = Primary. Sens = Sensitivity. ETD = early treatment discontinuation.

^a The earliest date should be used if multiple dates are listed.

^b When summarising AEs leading to discontinuation, no upper cut-off day windows (i.e., 4 days and 30 days from last dosing date for AEs and SAEs respectively) are applied.

^c For safety laboratory tests sensitivity analysis is used for marked laboratory abnormality summaries only.

^d Only for analyses that exclude data after rescue.

^e The randomised withdrawal period starts from either Week 32 or Week 40 depending on the visit the third randomisation occurred at.

^f These sensitivity analyses use data up to Week 32 to exclude data from the randomised withdrawal analyses.

For analyses using data up to Week 32, in cases where Week 32 visit date is missing an imputed Week 32 date will be derived using the earliest possible date of the following:

- Week 26 date (target day 183) extrapolated to estimate the Week 32 date (target day 225)
- Third randomisation date
- Next visit date after Week 32

For analyses presenting the post-study visit, non-treatment follow-up visits or Week 104, no cut-off dates apply. Unscheduled Week 104 visits will be summarised as Week 104.

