3.7.2 Rescue Guidelines for Subjects with Protocol-Defined Lack of Glycemic Control

During the course of the trial, subjects may be eligible for the addition of open-label rescue medication to their blinded treatment regimen in order to treat ongoing hyperglycemia. Insulin may be used as rescue, at the Investigator's discretion. Subjects who were already taking insulin at the start of the study may be switched to a flexible insulin dose following a Rescue Visit. For subjects on baseline insulin, persistently increased doses of insulin 20% or more above baseline dose, despite advice and counsel to keep the insulin dose stable, may be considered another potential manifestation of poor glycemic control, and should be evaluated for rescue. Only insulin may be used as rescue medication, but subjects can be rescued without the use of medication.

Pre-specified glycemic criteria (see Table 3.5.2-1), based upon self-monitoring blood glucose (SMBG) FPG, or single central laboratory FPG and repeat confirmatory FPG have been established during the treatment period, starting at Week 6, and up to, but not including, the Week 52 visit, to determine eligibility for open-label rescue medication. Any permanent changes in dose of basal insulin should be done after evaluation of rescue criteria, including both SMBG and central laboratory FPG values. To maintain study integrity, plasma glucose samples used to determine eligibility for rescue must reflect fasting values. Subjects who are not fasting at the time of sample collection will be asked to return when in a fasting state.

Table 3.5.2-1: Lack of Glycemic Control Criteria for Initiation of Rescue Medication

| Study week | Rescue criterion |
|---|--|
| Week 6 visit up to and not including Week 26 visit | FPG>13.3 mmol/L (240 mg/dL) based on 3 consecutive fasting SMBG values followed by a confirmatory central laboratory FPG or Single central laboratory FPG followed by a confirmatory central laboratory FPG |
| Week 26 visit up to and not including Week 52 visit | FPG>10 mmol/L (180 mg/dL) based on SMBG for 3 consecutive days followed by a confirmatory central laboratory FPG or Single central laboratory FPG followed by a confirmatory central laboratory FPG or HbA1c >8.0% (while HbA1c values will remain blinded throughout the study, sites will be notified to allow rescue if values exceed this threshold) |

Subjects must be rescued following one of these scenarios:

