5 STUDY ASSESSMENTS AND PROCEDURES

Study procedures and their timing are summarized in Section 5.1.

The Investigator will ensure that data are recorded on the eCRFs. The electronic data capture (EDC) system will be used for data collection and query handling.

The Investigator ensures the accuracy, completeness, legibility, and timeliness of the data recorded and of the provision of answers to data queries according to the Clinical Study Agreement. The Investigator will sign the completed eCRFs. A copy of the completed eCRFs will be archived at the study site.

Immediate safety concerns should be discussed with the Sponsor immediately upon occurrence or awareness to determine if the subject should continue or discontinue study drug.

Adherence to the study design requirements, including those specified in Section 5.1, is essential and required for study conduct.

If scheduled visits at clinical sites will be significantly impacted by the COVID-19 pandemic (e.g., there is a risk that the subject may be exposed to COVID-19 when visiting the site), home visits by study site personnel/vendor are allowed in countries where this is logistically feasible and considered acceptable. Before such a visit, a risk assessment that considers the potential risks to both the subject and the study personnel has to be performed.

All screening evaluations must be completed and reviewed to confirm that potential subjects meet all eligibility criteria. The Investigator will maintain a screening log to record details of all subjects screened and to confirm eligibility or record reasons for screening failure, as applicable.

Procedures conducted as part of the subject's routine clinical management (e.g., blood count) and obtained before signing of the informed consent form may be utilized for screening or baseline purposes provided the procedures met the protocol-specified criteria and were performed within the time frame defined in Section 5.1.

Approximately 230 mL of blood will be collected from each subject. Repeat or unscheduled blood samples may be taken for safety reasons or due to technical issues with the samples.

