4.1.7.1 Visit windows

As subjects do not always adhere to the terms and conditions defined in the study protocol, visit windows will be used to assign each clinical assessment to a scheduled visit (for data that will be summarised by visit, as shown in [Table 9](#), [Table 10](#), and [Table 11](#)).

To apply the visit windows, note the following rules for defining the start and end of each study period:

- The ST period starts from Day 1 (start date of IP) and ends on the start date of the Week 26 visit or early discontinuation from the study, whichever is earlier. For subjects who did not enter the LT period, there is no cut-off date.
- For subjects entering the LT period, the LT period starts from the day after the end of the ST period and ends on the date of Week 56 visit or early discontinuation from the study, whichever is earlier.
- The Randomised Withdrawal period starts from the date of first intake of third randomisation treatment (i.e., IP issued on the Week 32 or Week 40 visit) and ends on the date of Week 56 visit or early discontinuation from the study, whichever is earlier.
- The post-study period starts from the day after the end of the LT period and ends on the date of Week 104 visit or date of lost to follow-up, whichever is earlier.

For subjects who entered the LT period but skipped the Week 26 visit, then the event date from the Continuation Long Term Follow up CRF will be used (if available). For subjects who entered the post-study period but skipped the Week 56 visit, then the latest visit date during the ST+LT period will be used to extrapolate the estimated Week 56 date (target day 395).

Prior to slotting the data must be restricted to the cut-offs defined for each variable and period as per [Table 8](#). Slotting must be repeated for each type of analysis applicable to a variable (primary and each sensitivity analysis).

Visit windows for post-baseline (after Day 1) assessments that will be slotted for the ST period are shown in [Table 9](#). Visit windows for assessments that will be slotted for the LT and randomised withdrawal period and the post-study (Week 104) visit are shown in [Table 10](#) and [Table 11](#).

Table 9 Visit windows for ST period assessments

Visit	Target Day	Day Range by Type of Assessment		
		Vital Signs	Safety laboratory panel, FPG, HbA1c, PK/PD ^a , Urinary glucose, Height, Weight	Growth and maturation markers, Tanner staging, ECG, Fasting lipid panel
Week 6	43	2 to 64	2 to 64	

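### The Week 26 HbA1c/FPG window closes on the visit start date, so a valid next-day redraw can be lost and the child imputed as if off drug

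*SAP*

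**What the plan says.** SAP Table 8 (Section 4.1.7) gives the ST cut-off for the primary HbA1c and FPG analyses as "Start of LT period (if applicable". Section 4.1.7.1 supplies the dates. The ST period "ends on the start date of the Week 26 visit or early discontinuation from the study, whichever is earlier". "For subjects entering the LT period, the LT period starts from the day after the end of the ST period". The order of work is fixed: "Prior to slotting the data must be restricted to the cut-offs defined for each variable and period".

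Table 9 runs the Week 26 window for HbA1c and FPG from Day 163 to the Week 26 visit or early study discontinuation. Table 10 opens the Week 32 window on the first LT day and closes it at Day 252, or at the first third-randomisation dose if that is earlier. Within a window the value nearest the target day is used, and unscheduled samples are eligible.

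Two special cases are covered. "For subjects who entered the LT period but skipped the Week 26 visit, then the event date from the Continuation Long Term Follow up CRF" is used in place of the visit date. And "For subjects who did not enter the LT period, there is no cut-off date".

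Missing Week 26 values go to multiple imputation (SAP 4.1.12). Only fasting FPG is analysed (SAP 3.2). Protocol Section 5 allows redraws: "Repeat or unscheduled blood samples may be taken for safety reasons or due to technical issues with the samples".

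**The concern.** The Week 26 value carries the primary endpoint, and its window is the only HbA1c/FPG window before Week 52 with no days after the visit. A failed or non-fasting sample that is redrawn the next day is a good measurement of a child still on the same blinded treatment. The rule moves it to Week 32, where it competes with the scheduled Week 32 sample and will normally lose because it lies further from Day 225.

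If Week 26 is then empty, both primary imputation models treat the child as someone no longer on drug. The error is therefore directional. It affects the primary HbA1c test, the FPG tests in the hierarchy, and the responder tests derived from imputed HbA1c.

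**Working it through.** **1. Date rule.** Let V be the study day on which the Week 26 visit starts, for a child entering LT. ST ends on V and LT starts on V + 1. A sample on day d is Week 26 if 163 ≤ d ≤ V. It is in the Week 32 window if V + 1 ≤ d ≤ 252.

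| V | V − 1 | V | V + 1 | V + 7 |
|---|---|---|---|---|
| 176 | Week 26 | Week 26 | Week 32 | Week 32 |
| 183 | Week 26 | Week 26 | Week 32 | Week 32 |
| 190 | Week 26 | Week 26 | Week 32 | Week 32 |
| 230 | Week 26 | Week 26 | Week 32 | Week 32 |

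The cut-off moves with the visit, so a late visit by itself loses nothing. What is lost is a sample dated after the visit started.

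**2. Comparison with the other windows.** The target days for HbA1c and FPG are 43, 85, 141, 183, 225, 281 and 365.

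| Between | Midpoint of targets | Last day of earlier window |
|---|---|---|
| Weeks 6 and 12 | 64 | 64 |
| Weeks 12 and 20 | 113 | 113 |
| Weeks 20 and 26 | 162 | 162 |
| Weeks 26 and 32 | 204 | Week 26 visit date |
| Weeks 32 and 40 | 253 | 252 |
| Weeks 40 and 52 | 323 | 322 |

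The HbA1c sensitivity row of Table 8 allows 8 days after the last ST dose. Its footnote takes the earliest listed date, so for an LT entrant still on drug the LT start comes first and the allowance has no effect.

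**3. What happens to the gap.** SAP 4.1.12.1 fills only missing values that have an observed value on both sides. Week 26 is the last visit in the ST imputation, so it passes to the second step. Under wash-out (4.1.12.3), an active-arm child is imputed from placebo Week 26 data using strata and baseline, and the child's own Week 20 value is not used. Under MI-RD (4.1.12.2), the donors are children who stopped treatment and returned at Week 26.

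**4. Size.** The plan's own figure comes first. Inputs from SAP 1.2 and 1.3 are a difference of 0.75, SD 1.7, 81 per arm and two-sided alpha 0.05. SE = 1.7 × √(2/81) = 0.267. Power = Φ(0.75/0.267 − 1.96) = 80.2% (79.7% by noncentral t with 160 df). The stated value of about 80% reproduces.

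Under wash-out, if a share f of active-arm Week 26 values is replaced by placebo-like values, the expected difference is 0.75 × (1 − f). The share f is my assumption. With the SE held fixed, noncentral t gives:

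| f | Children of 81 | Difference | Power |
|---|---|---|---|
| 0 | 0 | 0.750 | 79.7% |
| 2% | 1.6 | 0.735 | 78.1% |
| 5% | 4.1 | 0.713 | 75.5% |
| 10% | 8.1 | 0.675 | 70.9% |

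One child costs 0.75/81 = 0.009. If the loss cost only information, with 81 × (1 − f) per arm and no bias, the normal formula gives 79.4%, 78.1% and 75.9% for the same three shares.

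**The case against.** A reader might infer that any late or repeated Week 26 sample is thrown away and imputed. The documents do not support that. A repeat does no harm if the first sample was valid. An unscheduled value from Day 163 onward can serve, and the late sample is re-slotted rather than deleted. Imputation needs an unusable visit-date sample and nothing else in the window.

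The routes to such a gap are also narrow. The protocol rule "Subjects who are not fasting at the time of sample collection will be asked to return when in a fasting state" (Section 3.7.2) is written for glucose samples that decide rescue, not for the endpoint draw, and gives no reason to redraw HbA1c. Section 5 allows home visits during the pandemic but does not describe splitting one visit over several days. For HbA1c, what remains is a failed sample redrawn on a later day.

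The strict boundary has a purpose too. The later, tighter rescue criteria begin at the Week 26 visit, and a same-day cut keeps treatment started on those results out of the Week 26 value. This has some force for FPG. It has less for the primary analysis, whose estimand includes data after rescue.

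The plan also has safeguards. It tabulates missing HbA1c and FPG by visit, runs a tipping-point analysis on HbA1c, and has a missing-at-random sensitivity analysis that uses earlier visits. These make a problem visible, but they do not change the primary result.

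**Conclusion.** The point holds in a limited form. For LT entrants the stated rule excludes a valid redraw dated even one day after the Week 26 visit start. When no other usable value exists from Day 163, an on-drug child is imputed as off drug. Under wash-out the bias is toward no effect. Under MI-RD the same direction rests on the assumption that discontinuers have lost some drug effect by Week 26.

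The size is 0.009 per affected active-arm child under wash-out, assuming a uniform effect of 0.75. The documents give no rate of unusable or redrawn Week 26 samples. I expect it to be low for HbA1c and higher for FPG, where only fasting values count. The 5% and 10% rows show sensitivity and are not forecasts. It would be wrong to conclude that the trial is underpowered or that a stated sample-size figure is in error.

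A reader might also infer that children who do not enter LT have no upper limit at all. Table 9 does bound their window at the Week 26 visit or study discontinuation. The two texts conflict only for a child who stops drug, stays in the study, does not enter LT and misses Week 26. A later follow-up sample could then be taken as Week 26 if no nearer one exists. This needs reconciling but affects few children.

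**What to change.** In Table 8, Section 4.1.7.1 and Tables 9 and 10, add one rule. When there is no usable HbA1c (or fasting FPG) value on the Week 26 visit date, a sample labelled Week 26, or its repeat, counts as Week 26 if it is taken within 7 days after that date and before any third-randomisation dose. Seven days matches the visit window in Protocol Table 5.1-2. The Week 32 window for that variable then starts after the accepted sample. Treatment assignment does not change in this interval, because the third randomisation is at Week 32 at the earliest.

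Separately, state which upper limit applies to a child who stays in the study without entering LT and has no Week 26 visit, so that 4.1.7.1 and Table 9 agree. I would not impose a fixed day cap at the midpoint. It would drop observed off-treatment values that the ITT estimand uses, and it could push retrieved drop-outs below the five needed for MI-RD.

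The cost is SAP wording and slotting code. A few values will be up to 7 days later, and some may follow rescue triggered at Week 26. The primary estimand includes such values, and they can be flagged in the listings. No sample-size or power statement changes.
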